## Prior Therapy

14. Prior radiotherapy within 2 weeks of start of study intervention. Subjects must have recovered from all radiation-related toxicities and not require corticosteroids (up to 4 mg/day dexamethasone or equivalent will be allowed provided dose is stable for at least 30 days prior first SUPLEXA dose and remains stable throughout the trial), and not have had radiation pneumonitis. A 1-week washout is permitted for palliative radiation ( $\leq$ 2 weeks of radiotherapy) to non-CNS disease.
15. Transfusion of blood products (including platelets or red blood cells) or administration of colony stimulating factors (CSF) (including granulocyte CSF [GCSF], granulocyte-macrophage CSF [GMCSF], or recombinant erythropoietin) within 4 weeks prior to baseline.
16. Any vaccines (live, attenuated, inactivated or research vaccines) within 30 days of dosing with study intervention (refer to Section [6.8.1](#) for prohibited vaccines).

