### Overall Design

This is a FIH Phase 1, non-comparative, open-label, basket-design study. The study will consist of 2 cohorts:

- Solid tumours cohort: This cohort will include subjects with histologically or cytologically confirmed measurable solid tumours (e.g., various squamous cell carcinomas (skin, cervical, vaginal, oesophageal, lung), melanoma, prostate, and breast cancer)), radiographically confirmed as Stage 2 to 4 cancer. Subjects must fulfill entry criteria and not be currently receiving or under the residual influence of immunosuppressive therapies.
- Haematologic malignancies cohort: This cohort will include subjects with histologically or cytologically confirmed multiple myeloma, lymphoma, and chronic lymphocytic leukemia (collectively termed as haematologic malignancies for the purposes of this protocol). Subjects must fulfill entry criteria and have relapsed or refractory advanced malignancy for which no standard therapy exists.

A Data Safety Monitoring Committee (DSMB) will provide oversight of the study and will monitor safety on a regular basis throughout the study to recommend on any modification of the study. Refer to Section [9.3.6](#).

The study will be comprised of 3 periods. Screening, Treatment and Follow-up. Throughout the study, subjects will be evaluated as specified in the Schedule of Activities (SoA) in Section [1.3](#). Study schema is provided in [Figure 2](#).

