#### Type of Subject and Disease Characteristics

##### Solid Tumours

2. Histologically or cytologically confirmed diagnosis of locally advanced or metastatic solid tumour.
3. Have 1 or more tumours measurable based on RECIST v1.1 as assessed by the local site Investigator. Radiographic scans should be obtained within 5 weeks of Screening. Lesions situated in a previously irradiated area are considered measurable if objective progression has been demonstrated following radiation to such lesions.
4. Subjects who did not attain a durable response after receiving at least one standard/approved therapies which may include chemotherapy, targeted agents, radio-, immuno- conjugates, check point inhibitors or where there is no approved therapy. This includes subjects who attained a long-term stable disease (SD), or partial response (PR) are eligible. Long term SD subjects on a checkpoint inhibitor may continue checkpoint inhibitor (CPI) therapy.  
\* Any therapies defined as immunosuppressive require a washout period of at least 4 weeks, defined as 4 weeks (28 days) prior to blood collection for SUPLEXA manufacturing and any SUPLEXA dose administration.

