#### **Medical Conditions**

1. Known central nervous system (CNS) metastases and/or carcinomatous meningitis.
2. Prior allogeneic transplant.
3. Diagnosis of immunodeficiency or is receiving chronic and non-physiological, systemic steroid therapy or any other form of immunosuppressive therapy.
4. Active uncontrolled bacterial, viral, or fungal infection requiring systemic therapy at screening or Day 1.
5. History or current evidence of any condition, therapy, or laboratory abnormality that might confound the results of the study, interfere with the subject's participation for the full duration of the study, or is not in the best interest of the subject to participate, in the opinion of the treating Investigator.
6. Any unresolved Grade 2 or greater reversible toxicity from a previous anticancer therapy except for alopecia or Grade 2 neuropathy.
7. Clinically significant cardiovascular disease, including any of the following:

- a. Stroke or myocardial infarction within 6 months prior to first dose in the study.
- b. Presence of unstable angina within 6 months prior to first dose in the study.
- c. Congestive heart failure of New York Heart Association Grade 2 or higher.
- d. History or presence of clinically significant ventricular arrhythmias, or conduction abnormality; presence of clinically significant atrial fibrillation and resting bradycardia.
- e. Corrected QT interval (QTcF) of  $>450$  msec (males) or  $>470$  msec (females) using Fridericia's correction formula.
- f. History of congenital long QT syndrome.

8. Known history of testing positive for human immunodeficiency virus (HIV), and/or positive test for Hepatitis B virus surface antigen (HBsAg) and/or positive Hep C antibody result with detectable hepatitis C virus (HCV) ribonucleic acid (RNA) indicating acute or chronic infection.

*Note: Subjects who have been vaccinated against Hepatitis B and hence are positive only for the Hepatitis B surface antibody are permitted to participate in the study.*

9. A serious non-malignant disease (e.g., psychiatric, substance abuse, uncontrolled intercurrent illness, etc.) that could compromise protocol objectives in the opinion of the Investigator and/or the Sponsor.

10. At high risk of developing TLS per ([Cairo, 2010](#)). Specifically:

- a) Burkitt's lymphoma
- b) ALL with LDH  $\geq 2 \times \text{ULN}$  or WBC  $\geq 100 \times 10^9$  per  $\mu\text{L}$ .
- c) AML with WBC  $\geq 100 \times 10^9$  per  $\mu\text{L}$ .

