## Prior/Concurrent Clinical Study Experience

17. Participation in another clinical study of an investigational agent during the 2 weeks of this study's screening period.

*Note: Subjects participating in an observational study are an exception to this criterion and may qualify for the study with Sponsor approval.*

*Note: Subjects who have entered the follow-up Period of an investigational study may participate if 14 days have elapsed since the last dose of the previous investigational agent before blood is drawn for this study.*

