## 6.8 CONCOMITANT GENERIC THERAPY

Any medication or vaccine (including over the counter or prescription medicines, vitamins, and/or herbal supplements) that the subject is receiving within 4 weeks before the first dose of study intervention through 24 weeks after the last dose of study intervention must be recorded along with:

- Name of medication/therapy (generic name)
- Reason for use
- Dates of administration including start and end dates
- Dosage information including dose and frequency

Concomitant medications administered 24 weeks after the last dose of study intervention should be recorded for SAEs.

Concomitant medications necessary for the health and well-being of the subject and that do not interfere with study assessments are permitted during the study at the Investigator's discretion. All treatments that the Investigator considers necessary for a subject's welfare may be administered at the discretion of the Investigator in keeping with the community standards of medical care. This includes the use of appropriate medications for the treatment of AEs and/or concurrent illnesses under the direction of the Investigator. All medications must be recorded in the source and on the appropriate eCRFs. Start of new medications of any type (over the counter or prescription) during the study however is strongly discouraged as it can be deemed confounding.

Concurrent use anti-androgen therapies subjects with prostate cancer and anti-estrogen therapies for subjects with breast cancer is allowed. Bisphosphonate IV (i.e., zoledronic acid) or denosumab subcutaneous (SC) therapy must be initiated prior or within the first 60 days of the first administration of the study intervention. Oral bisphosphonate may be initiated at any point in the study for the treatment of osteoporosis.

Concurrent use of continued targeted therapies and immune checkpoint inhibitor therapies (e.g., anti-PD-1, anti-PD-L1 or anti-CTLA4) may be allowed provided the subject was on a stable dose for at least 3 months prior to enrolment and had at least a stable disease response.

Concurrent use of dexamethasone (up to 4 mg/day) may be allowed provided the subject was on a stable dose for at least 30 days.

The Sponsor's Medical Monitor should be contacted if there are any questions regarding concomitant or prior therapy.

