### 6.8.2 Prohibited Medications and Treatment

Medications or vaccinations specifically prohibited in the exclusion criteria are not allowed during the ongoing study. If there is a clinical indication for any medication or vaccination specifically prohibited during the study, discontinuation from study intervention may be required. The Investigator should discuss any questions regarding this with the Sponsor's Medical Monitor. The final decision on any supportive therapy or vaccination rests with the Investigator and/or the subject's primary physician. However, the decision to continue the subject on study intervention requires the mutual agreement of the Investigator, the Sponsor, and the subject. Subjects who, in the assessment of the Investigator, require the use of any of the prohibited treatments for clinical management should be removed from the study.

The following medications are excluded from concomitant use for all subjects during the study:

- Vaccines:

- Live vaccines including, but are not limited to measles, mumps, rubella, varicella/zoster, yellow fever, rabies, *Bacillus Calmette–Guérin* (BCG), and typhoid vaccine.
- Attenuated vaccines, e.g., FluMist®
- Inactivated vaccines, e.g., COVID-19 vaccine; Please also refer to Section 10.9 (Guidance to Address Global Health Emergencies)
- Research vaccines, including any investigative COVID-19 vaccine studies

Note: Seasonal influenza vaccines for injection are generally killed virus vaccines and are allowed.

- Concurrent use of immunostimulatory agents, including but not limited to IFN- $\alpha$ , IFN- $\gamma$ , or interleukin 2 (IL-2) with study intervention, during the entire study.
- Any investigational agent, other than SUPLEXA.
- Immunosuppressive anticancer therapies (chemotherapy, radiation therapy, biological therapy or immunotherapy which are not specified in this protocol) or approved by the Sponsor will be excluded. Herb supplements that are used for the treatment of the malignancy under the study are not allowed.

Note: Palliative radiation therapy for pain management or for symptomatic solitary lesion if not new lesion may be allowed at the Investigator's discretion.

*Note: Surgery to bone lesion to prevent the risk of fracture will be allowed.*

- Concurrent use of immunosuppressive medications, including but not limited to cyclophosphamide, azathioprine, or methotrexate.

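### The entry rules for radiotherapy and immunosuppressive therapy disagree on interval and anchor, so radiotherapy can follow the manufacturing blood draw and the baseline scan

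*Combined protocol and SAP*

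**What the plan says.** **Solid-tumour washout.** The footnote to inclusion 4 (Section 5.1) says that treatments in the immunosuppressive class "require a washout period of at least 4 weeks, defined as 4 weeks (28 days) prior to blood collection for SUPLEXA manufacturing". The same sentence goes on to apply the 28 days before any SUPLEXA dose as well, so the rule has two anchors. No definition of the class is given.

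**Where radiotherapy is classed.** Section 6.8.2 prohibits, during the study, "Immunosuppressive anticancer therapies (chemotherapy, radiation therapy, biological therapy or immunotherapy which are not specified in this protocol". A note there leaves palliative radiation to the investigator's discretion in some circumstances.

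**Radiotherapy.** Exclusion 14 (Section 5.2) bars "Prior radiotherapy within 2 weeks of start of study intervention" and accepts 1 week for palliative radiation outside the CNS. Its only anchor is the start of treatment.

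**Baseline scan.** Inclusion 3 accepts scans within 5 weeks of screening; note h of the Schedule of Activities says 4 weeks. Inclusion 3 also lets a lesion in a previously irradiated area count as measurable if it has progressed since the radiation.

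**Steroids.** Exclusion 3 bars anyone "receiving chronic and non-physiological, systemic steroid therapy or any other form of immunosuppressive therapy", with no exception. Section 6.8 states: "Concurrent use of dexamethasone (up to 4 mg/day) may be allowed provided the subject was on a stable dose for at least 30 days". Exclusion 14 contains a similar allowance.

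**Investigational agents.** Exclusion 17 speaks of a screening period of 2 weeks, while the Synopsis and Section 4.1.1 allow up to 5 weeks. Its note admits subjects in follow-up of another study "if 14 days have elapsed since the last dose of the previous investigational agent before blood is drawn for this study".

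**Cohort.** The 28-day footnote stands under the solid-tumour heading. The design statement that subjects must "not be currently receiving or under the residual influence of immunosuppressive therapies" is likewise only in the solid-tumour bullet of the Synopsis and Section 4.1.

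**The concern.** SUPLEXA is made from blood drawn at Screening Visit 1, up to 35 days before first dose, and tumour response is measured against the baseline scan. An interval counted only back from first dose protects neither time point. A site that follows exclusion 14 may accept a subject irradiated after the draw, after the scan, or both.

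The statistical stake is attribution. Under Appendix 5, a partial response is a fall of at least 30% in the sum of target-lesion diameters from baseline. If a target lesion is irradiated after the baseline scan, shrinkage from radiation enters that sum. Neither Section 9.3.2 nor Appendix 5 says what to do with such a lesion. Section 9.1 lets the sample size or the per-tumour cap grow if anti-tumour activity looks promising, so a misattributed response could bear on that decision.

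**Working it through.** The plan gives no figure of its own to reproduce here; this is date arithmetic on its stated windows.

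**Inputs.** 28 days before draw and before any dose (inclusion 4); 14 days, or 7 if palliative, before first dose (exclusion 14); draw at Screening Visit 1 and screening up to 35 days (Synopsis, Figure 1 title); scan up to 28 or 35 days before screening (note h, inclusion 3); about 8 subjects per tumour type (Section 9.1).

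**1. Shared anchor, first dose.** 28 − 14 = 14 days; 28 − 7 = 21 days. This conflict does not depend on when blood is drawn.

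**2. Relative to the draw.** Let L be the days from draw to first dose. Exclusion 14 allows radiotherapy up to max(0, L − 14) days after the draw, or max(0, L − 7) if palliative. The documents give only the maximum L = 35; the shorter values are assumptions that show the range.

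| L (days) | Latest radiotherapy after draw | Latest palliative radiotherapy after draw |
|---|---|---|
| 35 | 21 | 28 |
| 28 | 14 | 21 |
| 21 | 7 | 14 |
| 14 | 0 | 7 |
| 7 | 0 | 0 |

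**3. Relative to the scan.** Let s be the days from scan to consent, with a full 35-day screening. Exclusion 14 allows radiotherapy up to s + 35 − 14 days after the scan (palliative: s + 35 − 7).

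- s = 0: 21 (28) days
- s = 28: 49 (56) days
- s = 35: 56 (63) days

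**4. If the bar in Section 6.8.2 on radiation during the study covers screening.** The non-palliative route between consent and first dose closes. The palliative route stays open, as does the interval between a pre-consent scan and consent, which is up to 28 or 35 days.

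**5. If the 28-day rule is applied to all radiotherapy.** With the draw on the day of consent and a scan 35 days earlier, radiotherapy may still fall 35 − 28 = 7 days after the scan; with a scan 28 days earlier, 0 days.

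**6. Possible effect on ORR (illustration).** Using the exact Clopper-Pearson limits named in Section 9.3.2, 0 of 8 gives 0%, with upper limit 1 − 0.025^(1/8) = 36.9%. One response caused by radiation gives 1/8 = 12.5% (95% CI 0.3% to 52.7%). The documents do not say how often this would happen.

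**7. Secondary mismatches.** Steroids: a course stable for at least 30 days is hard to call anything but chronic, exclusion 3 gives no threshold for what is physiological, and neither passage refers to the other. Exclusion 17: 2 weeks of screening against up to 5. Haematologic cohort: inclusion 5 carries no washout, and no other criterion sets a fixed interval for prior chemotherapy.

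**The case against.** **The criteria are cumulative.** Sections 5.1 and 5.2 require every relevant inclusion criterion to be met and exclude on any exclusion criterion. If radiotherapy is immunosuppressive, a solid-tumour subject irradiated after the draw fails inclusion 4 whatever exclusion 14 says. This is right as logic, but the 2-week and 1-week allowances would then have no effect in that cohort, and sites cannot tell which was intended. It also does not fully close the scan route (step 5).

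**Section 6.8.2 is not a definition.** It lists prohibited concomitant therapies and is limited to those not specified in the protocol. Since exclusion 14 does specify radiotherapy, one may argue that the specific rule governs. This is a fair reading. It shows that the text supports two answers, which is the problem.

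**Radiation is barred during the study, and inclusion 3 has an irradiated-lesion rule.** The bar narrows the gap as in step 4 but leaves two routes open. The lesion rule looks back at lesions already irradiated and does not expressly cover radiation after the baseline scan.

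**Stronger readings that a reader might infer, and that the documents do not support:**

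- *A gap of 49 to 56 days.* With L = 35, inclusion 4 puts the last radiotherapy 35 + 28 = 63 days before first dose, and 63 − 14 = 49, 63 − 7 = 56. That compares different anchors at the longest lead time. On the shared anchor the gap is 14 or 21 days.
- *Haematologic subjects have no washout.* Exclusions 3, 6, 13, 14 and 17 apply to them too. Only a fixed interval for prior chemotherapy is missing.
- *The dexamethasone passages cannot both stand.* Exclusion 14 and Section 6.8 can be read as a specific exception to exclusion 3. What is missing is the cross-reference and a threshold.

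**Conclusion.** The point stands. Inclusion 4, read with Section 6.8.2, and exclusion 14 disagree by 14 or 21 days on the anchor they share. Exclusion 14 has no anchor at the draw or the scan. Under it, radiotherapy can fall 0 to 21 days after the draw (palliative: 0 to 28) as the lead time runs from 7 to 35 days, and it can fall after the baseline scan. A target lesion so irradiated could contribute to ORR.

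This rests on two assumptions: that radiotherapy belongs to the undefined immunosuppressive class, for which Section 6.8.2 is the best textual support, and that a site may act on exclusion 14 as written. The absence of a rule for lesions irradiated after baseline does not depend on how the class is defined. The steroid, exclusion 17 and haematologic-cohort points are secondary drafting gaps.

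This should be fixed, but it does not undermine the trial's main purpose: the primary endpoints are dose-limiting toxicities and adverse events, and ORR is secondary, non-comparative and descriptive.

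**What to change.** Reconcile inclusion 4, exclusions 3, 14 and 17, and Sections 6.8 and 6.8.2. State which therapies count as immunosuppressive. For each interval, state the anchor (draw, first dose or both) and the cohort to which it applies. Cross-reference the dexamethasone allowance and exclusion 3, and align exclusion 17 with the actual length of screening. All intervals, the steroid rule and whether any interval extends to the haematologic cohort are for the sponsor to decide.

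In the response analysis (Section 9.3.2 or the SAP), state that a lesion irradiated after the baseline scan cannot be a target lesion or support a complete or partial response unless a post-radiation baseline is available.

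The cost is a wording amendment with no added visits. A few subjects may have fewer target lesions or become non-evaluable for response.

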## Prior/Concurrent Clinical Study Experience

17. Participation in another clinical study of an investigational agent during the 2 weeks of this study's screening period.

*Note: Subjects participating in an observational study are an exception to this criterion and may qualify for the study with Sponsor approval.*

*Note: Subjects who have entered the follow-up Period of an investigational study may participate if 14 days have elapsed since the last dose of the previous investigational agent before blood is drawn for this study.*

## Other Exclusions

18. < 6 months life expectancy at the local site Investigator judgement.
19. Pregnant or breastfeeding female subjects within the projected duration of the study, starting with the first screening visit through 120 days after the last dose of study intervention.

### 5.3 SCREEN FAILURES

Screen failures are defined as subjects who consent to participate in the clinical study but are not subsequently entered in the study. A minimal set of screen failure information is required to ensure transparent reporting of screen failure subjects to meet the Consolidated Standards of Reporting Trials (CONSORT) publishing requirements and to respond to queries from regulatory authorities. Minimal information includes demography, screen failure details, eligibility criteria, and any SAE.

Individuals who do not meet the criteria for participation in this study for reversible reasons may be rescreened. A new subject number will be assigned upon rescreening. For more details on specific indications refer to the SUPLEXA IB.

## 6 STUDY INTERVENTION

Study intervention is defined as any investigational intervention(s), marketed product(s), placebo, or medical device(s) intended to be administered to a study subject according to the study protocol.

### 6.1 STUDY INTERVENTION ADMINISTERED

ARM Name	Active
Primary Intervention Name	SUPLEXA therapeutic cells (referred to as SUPLEXA throughout)
Type	Autologous cellular therapy comprised of ex vivo activated autologous PBMC comprised predominantly of NK, NKT, $\gamma\delta$ T cells, and T cells of both CD8-positive and CD4-positive types stored in cryogenic media.
Dose Formulation	PlasmaLyte with 28 mM glucose, 3.5% human serum albumin, 50% EZ-CPZ (a proprietary cryopreservative medium) and 10% dimethyl sulfoxide
Unit Dose Strength	Billion cells
Dosage Level(s)	Each subject in each cohort will receive a target 2.5 billion SUPLEXA cells (range 1.3 to 3.1 billion cells) per infusion of 100 mL of cryogenic preservative solution.
Route of Administration	IV
Administration instructions	
Administer weekly (QW) <math>\pm 2</math> days for the first 3 weekly infusion and thereafter weekly with a range of -1 day to +7 days.
 
For prophylactic pre-treatment, refer to Section 6.8.1.
 
Thaw a SUPLEXA IV infusion bag.
 
Into the SUPLEXA IV infusion bag, slowly transfer approximately 250 mL (250 grams) of diluent PlasmaLyte (<math>\pm 20\%</math> is within the acceptable range; i.e., 200-300 grams or mLs). Allow the fluid to transfer by gravity.
 
Infuse each individual bag's full volume within 60 minutes into the subjects.
 
Where doses of 2 bags (5B cells) is given the same process and time is used. Thus, infusion of 2 bags is within 2 hours (120min).
 
Subjects may ambulate after infusion is complete.
 
For the first 3 weekly infusions:

ARM Name	Active
	
 
The first 3 subjects in each cohort will be monitored closely at the clinic for at least 6 hours after each of the first 3 weekly infusions and be contacted by phone on a daily basis (weekdays) between weekly infusions for up to 5 days post the 3rd treatment.
 
After the first three subjects , any subject receiving SUPLEXA will require a minimally 90minute (+/- 30min) post infusion observation and will be monitored for any AEs and immediate post infusion reaction(s).
 
 
Refer to Pharmacy manual for detailed administration instructions.

Sourcing	Autologous SUPLEXA therapeutic cells are manufactured, labelled, stored, and distributed by selected Contract Manufacturing Organisation.
Packaging and Labelling	Packaging and labelling will be per local regulations.

